2.8.4.3 Changes in height, weight and head circumference

Summary statistics and change from baseline will be provided for weight, height, and head circumference (patients ≤ 3 years) by visit and age group (and overall). Subgroup analysis of height (i.e., height, z-score for height and age-adjusted percentile for height) will be performed for patients satisfying the criterion of being within the age range of 2-9 years at each 12-month visit throughout the OLE study and for overall group. Summary statistics by yearly visit will be provided.

In addition, age-adjusted percentile will be calculated for height, weight and BMI; Z-score will be calculated for height, as done by the WHO to assess child growth. For more details, see [World Health Organization \(WHO\) 1997](#).

The same summaries as for the raw values will be produced for these Z-scores. In addition, shift tables will be produced using the following rules for severe low/moderate low/normal classification ([Dibley et al, Mei Z and Grummer-Strawn LM, World Food Programme](#)):

- Z-score < -3: severe low
- -3 ≤ Z-score < -2: moderate low
- Z-score ≥ -2: normal

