**Table 8-1 Assessment Schedule**

Visit	500	501 **	502 *	503 *	504 *	505 *	50 6 †	507	508 †	509	510 †	511	512 †	513	514 †	515	516 †	517	518 520 522 †	519 521 523 †	U N S	599
Week/Month	Screening	Wk 0	Wk 2	Wk 4	Wk 6	Wk 8	Mo 3	Mo 6	Mo 9	Mo 12	Mo 15	Mo 18	Mo 21	Mo 24	Mo 27	Mo 30	Mo 33	Mo 36	Mo 39 Mo 42 Mo 45 Mo 51	Mo 42 Mo 48 Mo 54	EO S 	
Obtain Informed Consent (parent(s)-legal guardian(s)/consent-assent (patient, as applicable) 	x S																					
Demography	x																					
Inclusion/Exclusion Criteria	x	x 																				
Medical History	x																					
Pediatric Heart Failure History	s																					
Concomitant Medications 	x	x	x	x	x	x	x	x	x	x	x	x	x	x	x	x	x	x	x	x	x	
Vital Signs (BP and pulse)	x	x	x	x	x	x		x		x		x		x		x		x	x	x	x	
Height	x	x							s		x		s		x		s		x	s		
Weight	x	x	x	x	x	x		x		x		x		x		x		x	x	x	x	

Visit	500	501 **	502 *	503 *	504 *	505 *	50 6 †	507	508 †	509	510 †	511	512 †	513	514 †	515	516 †	517	518 520 522 †	519 521 523	U N S	599
Week/Month	Screening	Wk 0	Wk 2	Wk 4	Wk 6	Wk 8	Mo 3	Mo 6	Mo 9	Mo 12	Mo 15	Mo 18	Mo 21	Mo 24	Mo 27	Mo 30	Mo 33	Mo 36	Mo 39 Mo 42 Mo 45 Mo 51	Mo 42 Mo 48 Mo 54	EO S 	
Head Circumference (≤ 3 years old)		x							x			x					x		x		x	
Physical Examination (complete)	s	s								s			s				s		s		s	
Physical Exam (abbreviated)			s	s	s	s		s			s			s							s	s
Urinalysis	x 								x			x					x		x	(x)	x	
Serum/Urine Pregnancy Test 	x 	x	x	x	x	x		x		x		x		x		x		x		x	x	x
Complete Laboratories	x 								x			x		x		x		x		x 	(x)	x
Abbreviated Laboratories 		x 	x	x	x	x		x			x			x		x				x 	(x)	
AEs/SAEs	x	x	x	x	x	x	x	x	x	x	x	x	x	x	x	x	x	x	x	x	x	x
Dosage Administration Record		x	x	x	x	x	x	x	x	x	x	x	x	x	x	x	x	x	x	(x)	x	
Study Medication Compliance			s	s	s	s		s		s		s		s		s		s		(s)	s	

UNS = Unscheduled visit

S = assessment to be recorded on source documentation only

X = assessment to be recorded in the clinical database or received electronically from a vendor

PSD = Premature subject discontinuation

(x) / (S) = parentheses indicate that this is an optional assessment

† Visit numbers 506, 508, 510, 512, 514, 516, 518, 520, 522 are telephone visits.

 Patient Assent document is captured as a source document and is not stored in the clinical database.

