## **8.2 Subject demographics/other baseline characteristics**

Country specific regulations should be considered for the collection of demographic and baseline characteristics in alignment with eCRF.

Subject demographic and baseline characteristic data will be collected including: year of birth (where allowed) age in years (age in months for subjects < 2 years, where allowed), sex, race and ethnicity, as well as the Identification Number (ID No.) the subject was formerly assigned in the PANORAMA-HF study (CLCZ696B2319). Additionally, vital signs, weight and height will be collected. Relevant medical history/current medical condition data includes data until the start of study drug. (Information regarding pediatric heart failure history will be recorded only in source documentation.) HF medications will be recorded on the Concomitant Medications eCRF.

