## **8.4 Safety/Tolerability**

The Sponsor may request additional information on specific adverse events or laboratory events of interest and may make requests to perform additional diagnostic tests to further assess the safety profile of sacubitril/valsartan. Such information may include diagnostic procedure reports, discharge summaries, autopsy reports, and other relevant information that may help in assessing the reported adverse event. All additional information will be de-identified prior to collection by Novartis or its agents.

In addition to AE/SAEs, the following safety-related evaluations will be done:

- Physical examinations (data recorded only in source)
- Vital signs
- Height, weight, and head circumference (head circumference is only collected in subjects who are ≤ 3 years of age at enrollment)
- Laboratory evaluations
- Pregnancy
- Angioedema

Safety assessments are specified below with the assessment schedule detailing when each assessment is to be performed.

For details on AE collection and reporting, refer to AE section ([Section 10.1](#)).

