#### **12.4.1 Definition of primary endpoint(s)**

Adverse events, laboratory assessments, vital signs, and duration of drug exposure are considered primary endpoints.

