2.1 Data analysis general information

Unless otherwise specified, the data will be analyzed according to the study protocol using SAS 9.4 or higher and R 3.4.3 or higher, by Novartis personnel.

In general, continuous variables will be summarized using number of observations, mean, standard deviation, median, quartiles, minimum and maximum. Categorical variables will be summarized using frequencies and percentages. Unless otherwise specified, the by age group summaries will include: summary for the two age groups (6 years and older, 1 year to < 6 years) and summary for the entire analysis set.

Study completion is defined as having reached the end of study visit (December 2023 from Protocol Amendment V.01 and later versions or December 2022 for Protocol V.00) while on treatment, or having completed 12 months of study while being on treatment and being transitioned to commercial Entresto.

Data from all study centers will be combined.

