2.3.2 Demographics and baseline characteristics

Summary statistics will be provided by age group and for overall for demographics and baseline characteristics, including age, age group (only for overall), sex, race, ethnicity, weight, height, head circumference (for subjects \leq 3 years old), BMI, vital signs, age adjusted percentile for weight, height and body mass index (BMI = weight (kg) / height² (m²)), z-score for height .

Continuous variables will be summarized using n, mean, standard deviation, median, minimum, the first quartile (Q1), the third quartile (Q3), and maximum. Categorical variables will be summarized using frequencies and percentages. The SAF will be used for the above analyses.

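### Head circumference is summarised only as raw values and raw change, so in this single-arm study its mean change cannot separate normal from partly slowed head growth

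*SAP*

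**What the plan says.** SAP 2.8.4.3 plans the following for growth: "Summary statistics and change from baseline will be provided for weight, height, and head circumference", the last for patients up to 3 years, by visit and age group. It continues: "age-adjusted percentile will be calculated for height, weight and BMI; Z-score will be calculated for height". The z-score summaries and the shift tables (cut-offs -2 and -3) therefore apply to height alone. Baseline follows the same pattern. SAP 2.3.2 lists head circumference as a plain measurement, and then "age adjusted percentile for weight, height and body mass index" plus a z-score for height.

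SAP 2.1 sets the default statistics: "continuous variables will be summarized using number of observations, mean, standard deviation, median, quartiles, minimum and maximum". It uses two age strata, 6 years and older and 1 to under 6 years.

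Protocol 8.4 names head circumference among the safety evaluations and states who is measured: "head circumference is only collected in subjects who are ≤ 3 years of age at enrollment". Table 8-1 has the shorter label "Head Circumference (≤ 3 years old)". Protocol 6.1.3 describes a single treatment arm. Protocol 12.4.1 lists the endpoints: "Adverse events, laboratory assessments, vital signs, and duration of drug exposure are considered primary endpoints".

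**The concern.** Children's heads grow. In a single-arm study, a table showing that mean head circumference went up says little unless the reader knows how much it should have gone up. The SAP deals with this for height, weight and BMI by adjusting for age. Head circumference is the only one of the four growth measures left without such an adjustment.

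Nothing else in the plan fills the gap. There is no control arm, and neither document gives reference values or a notable-value rule for head circumference. The age strata do not help, because every child aged 3 or under at enrolment falls in the 1 to under 6 years group. The raw mean also depends on the mix of entry ages.

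At stake is whether a measurement the protocol chose to take in its youngest patients is reported in a form that can answer a question. Protocol 8.4.3 says the study will yield growth data over at least a year.

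**Working it through.** The plan states no figure for head circumference, so there is none to reproduce. The documents give neither normal head growth nor its spread. The main results below are therefore shares of the normal gain *g* (*g* > 0).

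**1. Mean change from baseline.** Let a share *p* of children be affected and let their growth slow by a fraction *s*. Then mean change = (1 - *p* × *s*) × *g*.

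| Scenario | *p* | *s* | Mean change |
|---|---|---|---|
| All slowed | 1 | 0.25 | 0.75*g* |
| All slowed | 1 | 0.50 | 0.50*g* |
| All slowed | 1 | 0.75 | 0.25*g* |
| Some arrested | 0.10 | 1 | 0.90*g* |
| Some arrested | 0.20 | 1 | 0.80*g* |
| Some arrested | 0.30 | 1 | 0.70*g* |

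Every entry is positive. Only the size of the gain carries information, and the plan offers nothing to compare it with.

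**2. Illustration in centimetres (all inputs assumed).** Entry ages are uniform over 13 to 36 months. Growth from age 1 follows *A*(1 - exp(-*k*(age - 1))), with (*A*, *k*) = (3, 0.5), (4, 0.7) or (5, 0.9). The mean 12-month gain is +0.73 to +1.31 cm with normal growth, +0.55 to +0.98 cm with growth slowed by 25%, and +0.36 to +0.66 cm with growth halved. The first two ranges overlap: a gain of +0.8 cm fits either normal or slowed growth, depending on which curve is true.

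**3. Do the quartiles and minimum help?** Assume a gamma-distributed gain with a between-child coefficient of variation (CV) of 0.2 to 0.4, proportional slowing and no measurement error.
- All children slowed by half: lower quartile 0.43*g* to 0.35*g*, minimum above 0. Nothing stands out.
- Some arrested: the minimum is 0. The lower quartile is 0.81*g* to 0.62*g* at 10% arrested, 0.71*g* to 0.47*g* at 20%, and 0 at 30% (it reaches 0 once more than about 25% are arrested).

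**4. Measurement error weakens the minimum.** Suppose every child grows normally, with gains normally distributed (CV 0.3) and an error SD of *e* × *g* per reading. The SD of an observed change is √(0.3² + 2*e*²) × *g*. The chance that the smallest of *n* changes is zero or below is 1 - Φ(1/SD)^*n*, with SD in units of *g*. For *n* = 30:
- *e* = 0.1: SD 0.332, chance 4%
- *e* = 0.2: SD 0.412, chance 21%
- *e* = 0.3: SD 0.520, chance 56%
- *e* = 0.4: SD 0.640, chance 84%

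From *n* = 15 with *e* = 0.1 to *n* = 60 with *e* = 0.4, the chance runs from 2% to 97%. A minimum at or below zero therefore need not mean arrest. The values of *e*, *n* and the CV are assumptions; a right-skewed gain lowers the figures at small *e*.

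**5. What the remedy has to cope with.** Follow-up varies from 1 to about 4.5 years (protocol 3), with a 4-year maximum in Germany (protocol 4.2). If the limit is 36 months at entry, the oldest age measured is (36 + 12)/12 = 4.0, (36 + 48)/12 = 7.0 or (36 + 54)/12 = 7.5 years. If it means completed years, these become just under 5.0, 8.0 or 8.5.

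Protocol 8.2 collects age in years, with "age in months for subjects < 2 years, where allowed". Entry ages start at 13 months, so those recorded only in years make up (36 - 24)/(36 - 13) = 12/23 = 52% of the entry-age span, or (48 - 24)/(48 - 13) = 24/35 = 69% under completed years. These are shares of the span, not of children.

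**The case against.** The strongest reply is that little depends on this table. Head circumference is not an endpoint, and protocol 12.4 plans no analysis of it, so the SAP already goes further than required. Growth in the same children is covered by height z-scores with shift tables and by weight and BMI percentiles. The events of special interest in SAP 2.8.1 include bone growth and cognitive impairment, and complete physical examinations include a neurological part. Because raw values are kept, a z-score could be derived later without prespecification. All of this stands and caps the weight of the point. None of it measures head growth or makes the planned table interpretable.

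The arithmetic for the mean is also an identity rather than evidence of harm: *p*, *s* and *g* are not in the documents. That is fair. It shows what the table cannot distinguish, not that slowing will occur. Nor can the documents show that the sources cited for height cover head circumference at these ages.

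Two stronger readings are tempting and should not be drawn.
- *The age limit is undefined.* SAP 2.8.4.3 and Table 8-1 do not say when age is judged. But protocol 8.4 fixes it at enrolment and SAP 2.1 follows the protocol, so the shorter labels contradict nothing.
- *The raw by-visit mean must always rise.* That holds for paired change or for the fixed enrolment cohort. If older children left the summary as they aged, the unpaired mean could dip. Protocol 8.4 excludes that reading.

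**Conclusion.** The point holds as a minor, optional improvement. As planned, mean change in head circumference is positive under both normal and partly slowed growth, and neither document supplies the norm needed to tell them apart. A uniform slowing of 25% to 75% leaves the mean at 75% to 25% of the normal gain. Its size in centimetres cannot be established, because normal growth, its spread and the number of children are not given.

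The conclusion rests on the protocol's fixed enrolment cohort and a positive normal gain. The statement that quartiles and minimum do not reveal partial slowing further assumes roughly proportional slowing.

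A reader might infer that the minimum will reliably expose arrested growth. It may hint at it, but measurement error can produce the same value in a normally growing group. A reader might also infer that the safety conclusions are unsound. They are not affected: head circumference is not among the primary endpoints, and the gap is confined to one descriptive summary.

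**What to change.** In SAP 2.8.4.3, and in 2.3.2 for baseline:
- Add an age- and sex-adjusted head-circumference z-score or percentile from a growth reference that the sponsor names and that covers this measure.
- Summarise value and change from baseline at the scheduled yearly visits.
- Keep measurements beyond the reference's age range as raw values only.
- Repeat the protocol's age-at-enrolment rule in the SAP, for consistency.
- Use the -2 and -3 shift categories only if the chosen reference supports them for head circumference.

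The cost is SAP wording, one derived variable and one table, plus a shift table if supported. Head circumference, age and sex are already collected, so trial conduct does not change.

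There are downsides. The group may be small. Where age is known only in whole years, z-score levels would be coarse; change is less affected, because the time between visits is known. A fall could not be attributed to the drug rather than to heart failure: protocol Table 10-1 lists failure to thrive among events common in this population.

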2.9 Pharmacokinetic endpoints

Not applicable. There are no PK analyses.

2.10 PD and PK/PD analyses

Not applicable. There are no PD and PK/PD analyses.

2.11 Patient-reported outcomes

Not applicable, there are no patient-reported outcomes.

2.12 Biomarkers

Not applicable, there are no biomarkers.

2.13 Other Exploratory analyses

Not applicable. There are no other exploratory analyses.

2.14 Interim analysis

No interim analysis is planned. However, the safety will be monitored through regular review of adverse events and related data.

3 Sample size calculation

There is no specific sample size required for the study. All patients who have completed the double-blind phase of the study PANORAMA-HF, as defined in the protocol Inclusion Criteria, and who meet all other Inclusion and Exclusion criteria, are eligible for the extension study.

4 Change to protocol specified analyses

None.

5 Appendix

5.1 Imputation rules

The missing or partially missing start/end date for AEs and prior/concomitant therapies will be imputed using the Novartis AGB global standard approach. Details will be provided in the study PDS.

If the visit date is missing, the scheduled date (per protocol) of the visit will be used.

5.1.1 Study drug

If the study drug start date is missing, then the planned start date will be used. If only the study start day is missing (but the month is known), then the study start day will be the 1st day of that month, unless the planned date of the first dose is in the same month, then it will be the planned date of the first dose.

5.1.2 AE date imputation

See [Section 5.1](#).

5.1.3 Concomitant medication date imputation

See [Section 5.1](#).

5.1.3.1 Prior therapies date imputation

See [Section 5.1](#).

5.2 Rule of exclusion criteria of analysis sets

Table 5-1 Protocol deviations that cause subjects to be excluded

Deviation ID	Description of Deviation	Exclusion from analyses
INCL01	No informed consent.	Excluded from all analyses.

Table 5-2 Subject classification

Analysis set	PD ID that cause subjects to be excluded	Non-PD criteria that cause subjects to be excluded
SCR	INCL01	Not applicable.
SAF	INCL01A and INCL01B	Not obtaining any study medication.

6 Reference

WHO Global Database on Child Growth and Malnutrition (Internet) Available from: [\[https://apps.who.int/iris/bitstream/handle/10665/63750/WHO_NUT_97.4.pdf\]](https://apps.who.int/iris/bitstream/handle/10665/63750/WHO_NUT_97.4.pdf) (Accessed 02 May 2019).

World Food Programme, 2005. A manual: measuring and interpreting malnutrition and mortality. Rome, World Food Programme.

Mei Z and Grummer-Strawn LM, 2007. Standard deviation of anthropometric Z-scores as a data quality assessment tool using the 2006 WHO growth standards: a cross country analysis. Bulletin of the World Health Organization, 85, pp. 441-448.
